## 2.0 STUDY OBJECTIVE

The objective of this research study is to collect data which demonstrates the ability of the Nu-V3 device to offer relief from one or more of the following symptoms: pain, anxiety, depression, and/or sleeplessness. The objective is to demonstrate the effectiveness of Nu-V3 for any or all of the four symptoms listed.

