## 4.0 STUDY PROTOCOL

The Nu-V3 Clinical Study is a prospective, single-arm, open-label, multi-center study using the Nu-V3 cranial nerve stimulation treatment device in patients with pain, anxiety, depression, and/or sleeplessness.

For this Phase I study, a total of 50-100 patients at multiple centers will be registered for study participation. Study participants are those who have signed the informed consent form, met the inclusion and exclusion criteria, and are enrolled in the study at one of multiple sites. Enrolled participants are stratified based on their pain, anxiety, depression, and/or sleeplessness symptom presentation at baseline and treated with the Nu-V3 device for 8 weeks, then observed for an additional 4 weeks. Interim analysis of reported data will be based on baseline stratifications and conducted at 4, 8, and 12 weeks during this time. Post study, participants will be given the chance to continue with an optional maintenance treatment with the Nu-V3 device per a 2-weeks on, 2-weeks off schedule, for an additional 12 weeks, with an 8-week observation.

Subjects enrolled onto the Nu-V3 Clinical Trial will undergo the following regimen:

- At the baseline visit, patients will be asked to complete study questionnaires (Appendix 11) regarding all of the following symptoms: pain, anxiety, depression, and/or sleeplessness, as well as their quality of life, active medications, medical history, and demographical information.
- At each subsequent visit, patients will be asked to complete study questionnaires regarding all the following symptoms: pain, anxiety, depression, and/or sleeplessness, as well as their activity level and quality of life.
- The sessions will begin with the Nu-V3 device being placed on the left ear and three small pads (non-invasive) being placed on the ear. Each Nu-V3 device

lasts for up to 14 days with a change in the pads approximately 7 days into the treatment.

- Each session takes approximately 15-20 minutes. The placement of the device takes approximately 5 minutes and the remaining time is spent verifying ePRO form completion, and evaluating the patient for all device effects.
- The Nu-V3 device is mobile and is worn externally on the left ear 24 hours a day during treatment, fitting comfortably behind the ear. An electrical signal is sent to the external ear through coated wire leads attached to the device and adhesive pads which attach to three sites on the ear.

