#### 4.1 Phase I Study Assessment Tables

Nu-Life Solutions Miniaturized Wearable Medical Technology - Nu-V3		Study Treatment Assessments Table										Nu-V3
		*Evaluations are completed weekly, every 7 days =3 days										
Evaluation*	Study Treatment											
	Week 1	Week 2	Week 3	Week 4	Week 5	Week 6	Week 7	Week 8	Week 9-11	Week 12		
Informed Consent	x											
Inclusion and Exclusion 	x											
Patient Registration 	x											
Medications Form 	x			x				x		x		
Patient Onboarding and Orientation 	x											
In office assessment	x	x	x	x	x	x	x	x		x		
New Device Placed	x		x		x		x					
Pad Replaced		x		x		x		x				
Treatment Forms 	x	x	x	x	x	x	x	x				
No Device									x	x		
ePRO Questionnaires 	x	x	x	x	x	x	x	x	x	x		
Patients' Global Impression of Change ePRO form (PGIC) 		x	x	x	x	x	x	x		x		
Providers' Global Impression of Change ePRO form (PGIC)		x	x	x	x	x	x	x		x		
Family Global Impression of Change ePRO form (PGIC)		x	x	x	x	x	x	x		x		
Optional Patient Media Testimony	x			x				x		x		

1. Inclusion/Exclusion, Registration, Medications, Treatment forms to be completed by site coordinator via online module.  
 2. Patient Onboarding and Orientation includes introductory demographics form, Nu-V3 patient training video  
 3. ePRO questionnaires completed on patient's mobile device: DQ-9 (baseline), PTB-7, PEG, GAD-7, PHQ-9, PROMIS 4a, PGIC  
 4. If patient consents to media testimony, site will collect via study collection process every 4 weeks.

Evaluation*	Post Study Intervention Assessments Table														
	*Evaluations are completed weekly, every 7 days ±3 days														
	Optional Maintenance Therapy										Long Term Follow Up				
Week 13	Week 14	Week 15-16	Week 17	Week 18	Week 19-20	Week 21	Week 22	Week 23	Week 24	Week 25	Week 26	Week 27-28	Week 29	Weeks 30-31	Week 32
Medications Form 				x			x			x					x
In office assessment	x	x		x	x		x	x							
New Device Placed	x			x			x								
Pad Replaced		x			x			x							
Treatment Forms 	x	x		x	x		x	x							
No Device			x			x			x	x	x	x	x	x	x
ePRO Questionnaires 	x	x		x	x		x	x	x	x		x			x
Patients' Global Impression of Change ePRO form (PGIC) 	x	x		x	x		x	x				X			X
Providers' Global Impression of Change ePRO form (PGIC)		x			x			x				X			X
Family Global Impression of Change ePRO form (PGIC)		x			x			x				X			X
Optional Patient Media Testimony		x			x			x				x			X

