## 8.0 STUDY ENDPOINT and DATA ANALYSIS

### 8.1 Primary Endpoints: Primary endpoints consisted of the following:

Safety: The primary safety endpoint is the occurrence of reported unanticipated problems involving risk to subjects or others (“UPIRTSOs”). These UPIRTSOs are defined as those problems which alter the risks to subjects or others. This includes any study suspensions or holds. The primary safety endpoint analyses will be based on a risk-benefit conclusion.

Effectiveness: The primary effectiveness endpoints are an overall change in median reported symptoms of pain, anxiety, depression, and/or sleeplessness via numeric rating scales at 8 weeks. This primary effectiveness is measured by median reported symptom changes in pain, anxiety, depression, and/or sleeplessness for respective stratified populations via the following validated tools: Pain - Pain Intensity and Interference (PEG\_Scale), Anxiety - Generalized Anxiety Disorder 7-item (GAD-7) scale, Depression - Patient Health Questionnaire (PHQ-9), Sleeplessness - PROMIS short form 4a, and overall improvement of quality of life (QOL) - Patient’s Global Impression of Change (PGIC).

The hypothesis-driven criterion of effectiveness is to show that there is a statistically significant reduction in the median reported pain, anxiety, depression, and/or sleeplessness levels of patients using the Nu-V3 device. The second criterion is intended to show that there is a statistically significant improvement in reported quality of life and perceived treatment benefit, secondary to overall reported symptom reductions of pain, anxiety, depression, and/or sleeplessness.

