### 8.2 Secondary Endpoints: Secondary endpoints consisted of the following:

Effectiveness: The secondary effectiveness endpoint is an overall change in median reported symptoms of pain, anxiety, depression, and/or sleeplessness for respective stratified populations via numeric rating scales at 4, 8, and 12 weeks. This is measured via the following validated tools: Pain – Pain Intensity and Interference (PEG\_Scale), Anxiety - Generalized Anxiety Disorder 7-item (GAD-7) scale, Depression - Patient Health Questionnaire (PHQ-9), Sleeplessness - PROMIS short form 4a, and overall improvement of quality of life- Patient’s Global Impression of Change (PGIC).

The patient’s perceived treatment benefit and device comfort information will be captured via the non-validated tool, Perceived Treatment Benefit Form (PTB-7). This effectiveness tool will measure median levels of reported perceived treatment benefit and device comfort.

The hypothesis-driven criterion is to show that there is a statistically significant reduction in the median reported pain, anxiety, depression, and/or sleeplessness levels of patients using the Nu-V3 device at weeks 4, 8, and 12. The second criterion is intended to show that there is a statistically significant improvement in reported quality of life and perceived treatment benefit secondary to overall reported symptom reduction of pain, anxiety, depression, and/or sleeplessness at weeks 4, 8, and 12.

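### The primary symptom criterion does not say how many of four scales must succeed and has no alpha, test or multiplicity rule; the quality-of-life criterion demands significance on the PGIC without a null value

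*Protocol*

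**What the plan says.** Protocol 8.1 names the PEG, GAD-7, PHQ-9 and PROMIS 4a as the symptom tools at week 8. It words its first criterion as follows: "there is a statistically significant reduction in the median reported pain, anxiety, depression, and/or sleeplessness levels of patients using the Nu-V3 device". Protocol 2.0 gives the goal as: "The objective is to demonstrate the effectiveness of Nu-V3 for any or all of the four symptoms listed". The SAP repeats both.

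Section 8.1 describes the quantity in two ways, as "an overall change in median reported symptoms" and as "median reported symptom changes". The first can be read as a difference between two medians, the second as a median of individual changes.

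The second criterion in 8.1 also calls for statistical significance, this time for: "improvement in reported quality of life and perceived treatment benefit, secondary to overall reported symptom reductions of pain, anxiety, depression, and/or sleeplessness". Quality of life is measured by the PGIC.

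Protocol 8.2 and the SAP's Secondary Endpoints claim significance again, for "sleeplessness levels of patients using the Nu-V3 device at weeks 4, 8, and 12".

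On how significance is to be judged, the SAP contains only a generic results checklist, headed as optional. It prompts for a null hypothesis, method, threshold and multiplicity adjustment. In SAP Section 5.0 (Results) the primary effectiveness analysis is an insert-here line.

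**The concern.** A criterion that names four scales without a success rule, and uses the word significant without a level or a test, cannot fail in a defined way. The test, the quantity, the dataset and the winning scale could all be settled after open-label data and the planned interim looks have been seen. The Phase I label does not remove the problem: the SAP calls Phases I and II together the primary pivotal study for the De Novo request, and 8.1 calls the criterion hypothesis-driven.

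The quality-of-life criterion has a different defect. Significance needs a reference value, and an item that itself asks about change has none unless the plan supplies it. The plan does not.

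**Working it through.** The documents give no alpha, power, effect size, SD or sample-size calculation, so there is no planned figure to reproduce. What follows is the consequence of the text under stated assumptions.

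**Symptom criterion.** Inputs: four scales (Protocol 8.1); success on any of them (natural reading of 8.1 with 2.0); two-sided 5% per scale (assumed; the SAP checklist offers it only as an example). Only a reduction counts, so the per-scale chance is a = 0.025 and the cut-off is c = 1.96.

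- Independent scales: 1 − (1 − 0.025)^4 = 0.096.
- Equal correlation ρ: 1 − ∫ φ(t) Φ[(c − √ρ·t)/√(1 − ρ)]^4 dt = 0.078 at ρ = 0.5 and 0.065 at ρ = 0.7.
- If one-sided 5% per scale were used: 1 − 0.95^4 = 0.185, then 0.144 and 0.120.

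The scales are analysed in strata that need not contain the same people. Only shared participants create correlation between the test statistics.

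**Secondary criterion.** Four scales at three visits make 12 tests. With an assumed correlation of 0.7 between visits, simulation gives at least one false reduction about 20%, 16% and 13% of the time at ρ = 0, 0.5 and 0.7.

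**After correction.** The first Holm step is 0.05/4 = 0.0125 per scale. Four independent tests at that level give 1 − (1 − 0.0125)^4 = 0.049 in both directions together, and correlation lowers it.

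**PGIC, by comparison of passages.**

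- The question in Appendix 11 asks about change since treatment began, so a pre-treatment answer has no meaning.
- Score 1 covers both no change and worsening, so worsening cannot be seen separately.
- In Protocol 4.1 the PGIC's own row is blank at Week 1 and starts at Week 2. But the general ePRO row is marked at Week 1 and its footnote lists PGIC, and section 4.0 says quality of life is asked at baseline. These places disagree.
- The provider note on the form treats 5–7 as a favourable score and a 2-point move from the last score as significant. Section 8.1 adopts neither, and neither supplies a null for a group test.

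The missing null decides the answer. Take an invented set of 50 scores with median 3 and 14 participants at 5–7. A one-sided signed-rank test gives p < 0.001 against a null of 1 or 2, p = 0.32 against 3 and p = 0.998 against 4. A responder test gives p = 0.013 against 15% and p = 0.11 against 20%.

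**Perceived treatment benefit.** The only dedicated tool appears to be the PTB-7, which both documents call non-validated. It stands under secondary endpoints in Protocol 8.2 and under primary endpoints in the SAP.

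**What multiplicity control cannot do.** Assume all four scales improve for reasons other than the device, with correlation 0.5, and that Holm is applied to signed-rank tests. At least one scale passes if the smallest p-value is at or below 0.0125. By simulation:

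| Non-device shift | n = 25 per stratum | n = 75 to 150 per stratum |
|---|---|---|
| 0.2 SD | about 17% | 45–76% |
| 0.3 SD | 32–33% | 80–98% |
| 0.5 SD | 74–75% | over 99% |

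**The case against.** The best defence of the symptom criterion is that *and/or* reflects enrolment. Participants enter with one or more symptoms and are analysed in the stratum for each, so every symptom could be its own claim. That is a possible partial reading. It means the documents should not be charged with stating that one significant scale is enough; they state no success rule at all. But section 2.0 points to the any-one reading, and nothing says that the four claims are separate.

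Several stronger statements are tempting and are not supported:

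- A reader might infer that the PGIC certainly has no baseline administration. Its own row and wording suggest so, but the Week 1 footnote and section 4.0 point the other way. This is a contradiction to reconcile.
- The two notes on the PGIC form need not conflict. One classifies a score and the other describes a move between scores, both as provider guidance on an individual patient.
- Protocol 8.1 does not name the PTB-7. The link from perceived benefit to that form is a reasonable inference.
- One could compute 21% if any of the SAP's Phase I, Phase II and Total columns could carry the claim, or a 95% pass rate for a PGIC test against the floor of 1. The columns are headings in a results template and the documents propose no floor test. Both figures are illustrations and carry no weight here.

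A final objection is that multiplicity is minor beside the lack of a control in a "prospective, single-arm, open-label, multi-center study". It stands as a limit on the remedy. It does not excuse an undefined test.

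**Conclusion.** The point holds. The primary symptom criterion has no success rule, alpha, sidedness, test or multiplicity rule. On its natural reading the chance of a false effectiveness claim is 6.5% to 9.6%, against 2.5% for one scale. Those figures rest on an assumed two-sided 5% per scale, zero true change and correlations from 0.7 down to 0. The quality-of-life criterion cannot be tested as written because no null is stated for an item that is itself a change score.

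The missing alpha, test, success rule and PGIC null must be fixed before the data are used for a claim. The level of the PTB-7, the unused provider notes and the baseline status of the PGIC are lesser clarifications. Even when corrected, the symptom tests can show change from baseline; they cannot by themselves show a device effect.

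**What to change.** **1. Symptom criterion.**

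- State two-sided 5% overall.
- Define each endpoint as within-participant change from baseline to week 8 in that symptom's own stratum. The visible text gives no score cut-off for membership, so fix it from baseline data before outcomes are seen.
- Test each by Wilcoxon signed-rank. Report the median change and the Hodges-Lehmann estimate with 95% CI, noting that the two agree only if changes are symmetric.
- Apply Holm to the four p-values and claim only the symptoms that pass.
- Name one confirmatory dataset in advance: Phase I, Phase II or Total.
- Label weeks 4 and 12 and all interim looks as descriptive, and word claims as change from baseline.

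**2. PGIC.** Replace the significance claim with the proportion scoring 5–7 at week 8 and an exact 95% CI. Reconcile the Week 1 footnote and section 4.0 with the PGIC row.

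**3. Perceived benefit.** Remove it from the primary significance criterion and give the PTB-7 one level in both documents.

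**Cost.** Wording only, with no added visits or participants. Power per scale falls at the first Holm step (0.05 to 0.0125). With signed-rank and an assumed normal 0.6 SD shift it goes from 80% to 60% at n = 25 and from 98% to 94% at n = 50. With strata of 75 to 150, as the Total dataset might provide, it stays at 99% or more. Weeks 4 and 12 lose their significance claims. The PGIC estimate is imprecise: at 40% responders the exact interval is 26–55% at n = 50 and 30–50% at n = 100.

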### 8.2 Secondary Endpoints: Secondary endpoints consisted of the following:

Effectiveness: The secondary effectiveness endpoint is an overall change in median reported symptoms of pain, anxiety, depression, and/or sleeplessness for respective stratified populations via numeric rating scales at 4, 8, and 12 weeks. This is measured via the following validated tools: Pain – Pain Intensity and Interference (PEG\_Scale), Anxiety - Generalized Anxiety Disorder 7-item (GAD-7) scale, Depression - Patient Health Questionnaire (PHQ-9), Sleeplessness - PROMIS short form 4a, and overall improvement of quality of life- Patient’s Global Impression of Change (PGIC).

The patient’s perceived treatment benefit and device comfort information will be captured via the non-validated tool, Perceived Treatment Benefit Form (PTB-7). This effectiveness tool will measure median levels of reported perceived treatment benefit and device comfort.

The hypothesis-driven criterion is to show that there is a statistically significant reduction in the median reported pain, anxiety, depression, and/or sleeplessness levels of patients using the Nu-V3 device at weeks 4, 8, and 12. The second criterion is intended to show that there is a statistically significant improvement in reported quality of life and perceived treatment benefit secondary to overall reported symptom reduction of pain, anxiety, depression, and/or sleeplessness at weeks 4, 8, and 12.

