## 4.2 Protocol Deviations

In the event the Nu-V3 device is inadvertently removed or the device comes off, the participant will contact the Principal Investigator. The Principal Investigator will determine the appropriate course of action to be taken.

If the study participant is unable to wear the device on their left ear, the study participant will be allowed to wear the device on their right ear, which will result in a minor study deviation. Left-ear deviations could be due to discomfort, sleep position, pain at the local site, or infection. A lack of significant improvement by the end of week 4, per the Principal Investigator's discretion, can also result in a deviation from left-ear placement.

Device placement should be recorded on the study treatment form within the electronic data capture system.

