### 8.3 Sub-Analyses: Sub-Analyses Consist of the following:

The sub-analyses endpoints consist of the mean number of weeks that pain, anxiety, depression, and sleeplessness response are achieved and sustained, without utilization of another device, during the 8-week intervention. In addition, study sub-analyses also include the mean number of weeks to initial benefit from Nu-V3 device use, and the mean medication dosage reduction of short acting pain, anxiolytics, and/or insomnia. The device's comfort-of-use, and patient's perceived treatment benefit will also be captured for sub-analyses.

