**Form PTB-7: Patient's Perceived Treatment Benefit**

[figure not shown]
For *initial assessment* of all symptoms, please rate your average symptom score prior to any treatment (i.e. over the last 30 days)

For any assessment *after treatment has been initiated*, please rate your global average symptom score since your last treatment

1. On a scale of 0-100%, how much benefit do you feel you have received from the Nu-V3 treatment in helping your symptoms?

2. How comfortable was the Nu-V3 device to wear?

3. Have you had any major discomfort from the device that has necessitated you to adjust the device placement?

\_\_\_\_ Yes  
\_\_\_\_ No

[figure not shown]
Subject ID \_\_\_\_\_ Date (dd/mmm/yyyy): \_\_\_\_/\_\_\_\_/\_\_\_\_

For *initial assessment* of all symptoms, please rate your average symptom score prior to any treatment (i.e. over the last 30 days)

[figure not shown]
For any assessment *after treatment has been initiated*, please rate your global average symptom score since your last treatment

4. Please rate your pain, anxiety, depression, and/or sleeplessness on a 0-10 scale:

[figure not shown]
Pain Level:

Anxiety Level:

Depression Level:

Sleeplessness Level:

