Phase II of the study consisted of 100-200 individuals who signed the informed consent form, met the inclusion and exclusion criteria, and were enrolled in the study at multiple sites. Enrolled participants are treated with the Nu-V3 device for 8 weeks, then observed for an additional 2 weeks. Interim analysis of reported data were conducted at 4, 8, and 12 weeks during this time. Post study, participants were given the chance to continue with an optional maintenance treatment with the Nu-V3 device per a 2-week on, 2-week off schedule, for an additional 12 weeks, with an 8-week observation.

Subjects enrolled onto the Nu-V3 Clinical Trial underwent the following regimen:

- At the baseline visit, patients will be asked to complete study questionnaires regarding all of the following symptoms: pain, depression, anxiety, and/or sleeplessness, as well as their activity level, active medications, and demographics information.
- At each subsequent visit, patients will be asked to complete study questionnaires regarding all the following symptoms: pain, depression, anxiety, and/or sleeplessness, as well as their activity level.
- The sessions will begin with the Nu-V3 device being placed on the ear and three small pads (non-invasive) being placed on the ear. Each Nu-V3 device lasts for up to 14 days with a change in the pads approximately 7 days into the treatment.
- Each session takes approximately 15-20 minutes. The placement of the device takes approximately 5 minutes and the remaining time is spent verifying assessment form completion and checking for any immediate effects from the device.
- The Nu-V3 device is mobile and is worn externally on the ear 24 hours a day during treatment, fitting comfortably behind the ear. An electrical signal is sent to the external

ear through coated wire leads attached to the device and adhesive pads which attach to three sites on the ear.

- Participants should be able to perform their typical day-to-day activities while wearing the device. They may shower while wearing the Nu-V3 device, provided that they do not get the device wet and use the small disposable ear covers that are provided for them.
- Patients should not change their existing forms of treatment or medications without discussion with the investigator.

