Risks to Health: Potential unanticipated problems require prompt reporting to Aspire IRB. These problems potentially place subjects or others at greater risk of physical or psychological harm than was previously recognized, and warrant consideration of substantive changes in the protocol or informed consent process or other action in order to protect the safety, welfare, or rights of participants. Aspire IRB must be notified within 5 calendar days of the event. The completed IRB Unanticipated Problem form (Appendix 3) must be received by Aspire IRB within 10 calendar days of the event. Unanticipated problems are defined as those problems which alter the risks to subjects or others. This includes any study suspensions or holds. This form will be used to report any problem that is unforeseen or involves risk. One form will be used per event or problem.

Table 4.1: Unanticipated Problems Involving Risk to Patients or Others			
	Phase I	Phase II	Total
UPIRTSO 1 (number)			
UPIRTSO 2 (number)			
UPIRTSO 3 (number)			
Overall UPIRTSOs Reported			

Table 4.2: Risk/ Mitigation Measures	
Identified Risk	Mitigation Measures

Insert Safety Analysis Here

Section 5.0: Results

Results: The principal safety and effectiveness results from patients in the Nu-V3 study are provided below. The primary safety analysis was based on all patients registered and included all reported UPIRTSO events. The primary safety endpoint included imputation for missing clinical outcomes data using the logistic regression method. The imputation model included baseline characteristics including age, sex/gender, marital status, primary language spoken, race/ethnicity, education history, and veteran status.

Primary Safety Endpoint:

Insert Primary Safety Endpoint Statistical Analysis

Insert Primary Safety Endpoint Statistical Table

Primary Effectiveness Endpoint:

Insert Primary Effectiveness Endpoint Statistical Analysis

Insert Primary Effectiveness Endpoint Statistical Table- 8 weeks

Secondary Effectiveness Endpoint:

Insert Primary Effectiveness Endpoint Statistical Analysis

Insert Primary Effectiveness Endpoint Statistical Table: 4, 8, 12 weeks

Sub-Analyses:

Insert Sub-Analyses Statistical Analysis

Insert Sub-Analyses Statistical Tables

Special Controls:

Insert Special Control Section Here

Benefit/Risk Determination:

Insert Benefit/Risk Section Here

Section 5.0: Administrative Information

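### PTB-7 item 3 counts major discomfort only when it led to a placement adjustment, and the plan names no suitable summary for this Yes/No item

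*Protocol*

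**What the plan says.** PTB-7 has two questions bearing on comfort. Item 2 asks "How comfortable was the Nu-V3 device to wear"; its response format is not visible in the copy reviewed. Item 3 asks "Have you had any major discomfort from the device that has necessitated you to adjust the device placement" and offers only Yes or No.

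On analysis, Protocol 8.2 says of PTB-7: "This effectiveness tool will measure median levels of reported perceived treatment benefit and device comfort". The SAP repeats the sentence but places it under the primary endpoints, whereas the protocol has it under the secondary endpoints. Neither document says which items it covers.

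Protocol 8.3 mentions comfort again, saying that it and perceived benefit "will also be captured for sub-analyses", and names no statistic. The corresponding place in the SAP's results section is a placeholder: "Insert Sub-Analyses Statistical Analysis".

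Outside PTB-7, Protocol 4.2 recognises discomfort as a reason for changing ears: "Left-ear deviations could be due to discomfort, sleep position, pain at the local site, or infection". Placement is recorded on the treatment form. No analysis of those records is stated.

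**The concern.** There are two separate weaknesses.

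The first is in the question. Item 3 is double-barrelled: Yes requires both major discomfort and a resulting adjustment. A No therefore mixes patients without major discomfort with patients who had it and left the device in place. Once the answer is recorded, no analysis of item 3 can separate them. The device is meant to be worn around the clock for eight weeks, so tolerated discomfort is a plausible experience and one that a comfort measure should show.

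The second is in the analysis. The one statistic named for comfort does not suit a Yes/No answer, and nothing else is specified for item 3. Either an uninformative summary is used, or the summary is chosen after the data are seen. The SAP describes the study as the pivotal support for a De Novo request, so a comfort statement drawn from this form could reach a regulator.

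**Working it through.** The documents give no expected discomfort rate and no sample-size calculation, so there is no planned figure to reproduce.

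**Inputs.** Protocol 4.0, Phase I: "a total of 50-100 patients at multiple centers will be registered for study participation". SAP, Phase II: "Phase II of the study consisted of 100-200 individuals who signed the informed consent form". Item 3 is binary. All rates used below are assumptions.

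**1. What item 3 counts.**

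| Major discomfort | Adjustment made because of it | Truthful answer |
|---|---|---|
| Yes | Yes | Yes |
| Yes | No | No |
| No | – | No |

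Let D be the share with major discomfort and a the share of those who adjusted. The share answering Yes is D × a, so D = (share Yes)/a. With 20% Yes:
- a = 1 gives D = 20%.
- a = 0.75 gives D = 0.20/0.75 = 27%.
- a = 0.5 gives D = 0.20/0.5 = 40%.

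The values of a are assumed. The documents give no basis for choosing one.

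**2. What a median would do with item 3, if it were applied.** Code No = 0 and Yes = 1. For even N the median is the average of the two middle ordered values. It is 0 as long as the number of Yes answers is at most N/2 − 1.
- N = 50: 50/2 − 1 = 24, or 48%.
- N = 100: 100/2 − 1 = 49, or 49%.
- N = 200: 200/2 − 1 = 99, or 49.5%.

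At exactly N/2 Yes answers the median is 0.5, which has no meaning for a Yes/No item. For odd N the limit is (N − 1)/2; for N = 75 that is 37, or 49.3%.

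**3. How often it would read No.** With X ~ Binomial(N, p), the probability is P(X ≤ N/2 − 1).

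| True Yes rate p | N = 50 | N = 100 |
|---|---|---|
| 0.30 | 0.998 | 1.000 |
| 0.40 | 0.902 | 0.973 |

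**4. What a proportion would show instead** (assumed results, exact Clopper-Pearson 95% intervals).
- 10/50 = 20% (10.0% to 33.7%)
- 20/100 = 20% (12.7% to 29.2%)
- 24/50 = 48% (33.7% to 62.6%)
- 49/100 = 49% (38.9% to 59.2%)

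The median reads No in all four cases.

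**5. One visit against the whole treatment period.** If a share w answered Yes each week, independently between weeks, the share ever answering Yes over the seven ratings at Weeks 2–8 would be 1 − (1 − w)^7.
- w = 0.05: 1 − 0.95^7 = 30%.
- w = 0.10: 1 − 0.90^7 = 52%.

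This is illustrative only. The weekly rates are assumed, and independence is doubtful when the same patient rates the same device repeatedly. It shows only why per-visit and ever-affected shares should both be reported.

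**6. The on-device window.** In the assessment table of Protocol 4.1, pads are replaced at Week 8 and the no-device period begins with the Weeks 9–11 column, where the ePRO questionnaires are still marked. The last on-device week therefore falls between the Week 8 and Week 9 forms, and a Weeks 2–8 window would miss it.

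**The case against.** A reader might infer that the plan will report No for discomfort even if 49% of patients have major discomfort. The documents do not support that. No sentence applies the median to item 3, and the word levels fits item 2, or the 0–100% benefit rating in item 1, better than a Yes/No tick. The 48–49% limit also bounds Yes answers to a conditional question at a single visit. It does not bound the share of patients with major discomfort, which could be higher because of the item's wording.

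Nor does the form as a whole record such patients as free of discomfort. Item 2 is a separate comfort question on the same form, and a patient who did not move the device can still give a poor rating there. A median of item 2 does not show how the worst-off patients fare, but that is true of any median. With the response scale not visible, objecting to it would be a preference, not a fault in the plan.

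There are other routes as well. Protocol 4.0 has staff check for device effects at each session, and the weekly treatment form asks for a reason when the device is not on the left ear. These catch some discomfort, but no analysis of them is specified, and the ear question misses discomfort without a change of ear.

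Finally, PTB-7 is declared non-validated, the primary safety endpoint is unanticipated problems, and no decision rule depends on item 3. That argues for a lower severity. It does not remove the two weaknesses: the wording still loses information, and item 3 still has no stated summary.

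**Conclusion.** The point holds in a limited form. Item 3 undercounts major discomfort by construction; the size of the undercount depends on how many affected patients leave the device in place, which is unknown. The only statistic named for comfort would be uninformative for this item, reading No with up to 48% (N = 50) or 49% (N = 100) Yes answers at a visit. That figure is conditional on the median being applied to item 3, which the documents do not say. On the other reading, item 3 has no planned summary. Both readings call for the same change.

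The primary effectiveness test is unaffected, and I rate this minor to moderate. Including Week 9 assumes that item 3 is answered for the period since the previous form; the readable text of the item gives no recall period.

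**What to change.** - **Form.** Split item 3 into two questions. The first asks whether the patient had any major discomfort from the device, whether or not it was moved. The second, for those answering Yes, asks whether the placement had to be adjusted. State the recall period.
- **Protocol 8.2 and SAP.** Say which PTB-7 items the median covers and limit it to the graded ones. For each part of item 3, report the number and proportion of treated patients answering Yes, per visit and at any on-device rating, with exact 95% confidence intervals. Count the Week 9 form as an on-device rating.
- **Consistency.** Reconcile the placement of the PTB-7 sentence, which is under secondary endpoints in the protocol and primary endpoints in the SAP.

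The cost is small: one reworded item on a form that is already non-validated, and a few sentences in each document. Reporting proportions needs no new data. If enrolment has begun, answers before and after the rewording must be tabulated separately. The comfort result may also look less favourable.
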